9.4.2 Blood sampling in paediatric patients

In view of the lower circulating blood volume in children, the volume of blood obtained will be adjusted according to age in the following manner:

- Age 0-2 years: 1ml (maximum)
- Age 3-10 years: 5-10ml (maximum)
- Age 10-15 years: 20-30ml (maximum)

Samples for standard paediatric blood testing are collected in smaller tubes not routinely carried by LAA. To avoid introducing a new blood sampling protocol in the prehospital phase of care for a patient cohort that presents additional clinical challenges, prehospital blood collection will not be performed in paediatric patients.

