9.2. Screening and recruitment

All adult trauma patients (aged 16 and over) who are treated by London Air Ambulance, or trauma patients of any age who are admitted to the emergency department via a trauma team activation will be screened for eligibility to ACIT II. As most trauma patients will be incapacitated at the time of screening it is anticipated that a waiver of consent will be used followed by initiation of the informed consent process at a time appropriate from the participant as described in Section 9.1.

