9.4. Study Intervention

9.4.1 Blood samples

Trauma patients will have blood samples drawn to measure activation of coagulation, fibrinolysis, endothelial injury and the immune system. The maximum sample volume at each time point will be 40mls (maximum 30mls during bleeding time point samples). Samples will be collected in the Emergency Department at admission (Hour 0) and then 24±2 hours, 72±12 hours and at 7 days (±24 hours) post admission. Patients who are actively bleeding will have additional samples (30ml) taken after administration of the 4th, 8th and 12th units of red blood cells, if used.

Adult patients (>16 years old) treated by the London Air Ambulance medical team will have one additional sample taken in the prehospital phase upon their arrival and as close to the time of injury as possible. Prehospital samples will be prefixed PH to indicate a sample obtained prior to Hour 0 baseline (hospital admission) to ensure consistency with previous patients recruited to the ACIT II study.

Severe trauma patients not enrolled in the study would normally have blood samples drawn at minimum at 0, 12 and 24 hours and daily thereafter. Most trauma patients have blood tests drawn more frequently, especially those who have signs of hypoperfusion, coagulopathy, ongoing blood loss or those that are mechanically ventilated. As most major trauma patients have an arterial or central line placed, particularly during the first 24hours when the majority of samples will be taken, most blood draws will not be painful to the patient. When this is not the case, we will we will coordinate our blood draws with those of clinical need whenever possible, to minimise number of needle-sticks. We will not be able to use blood that has already been collected and placed into specimen tubes as our samples will require specific handling and processing.

Rationale for sequential blood sampling

(1) The activation pattern of coagulation following trauma is a dynamic process and the full picture will not be apparent on a single blood draw immediately following injury. Some coagulation factors are used up and the levels of others increased with increased genetic expression. Characterizing these patterns of altered coagulation

would have major implications for the treatment of coagulopathy. How this change occurs is currently unknown, but would be identified by this protocol.

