Patients will be considered eligible for enrolment in ACIT SWIFT if they fulfil all of the inclusion criteria and none of the exclusion criteria detailed below.

Inclusion Criteria

Patients eligible for screening are adult (>16 years) trauma patients enrolled into the SWIFT prehospital randomized controlled trial and are transported to a Major Trauma Centre in England, Wales or North Ireland

Exclusion Criteria

Any patient who fulfils any of these criteria will not be considered for inclusion in the study:

- Transfers from other hospitals
- Burns >5% total body surface area
- >120 mins have lapsed since time of injury
- Deemed inappropriate for recruitment by an independent clinician (e.g. mass casualty event or futility)

STUDY DESIGN

ACIT SWIFT is a prospective cohort multi-centre observational sub-study of ACIT II that will co-enroll patients who have been recruited into SWiFT. Through a data sharing agreement between SWiFT and ACIT SWIFT it will enable capture of patient data from injury in the prehospital phase of care (when dosing for SWiFT occurs) with a ACIT SWIFT blood sample on admission to the emergency department. Data for SWiFT will be collected for the first 28 days or hospital discharge. Biomarkers from the blood sample will be compared between treatment arms in SWiFT and correlated with patient injury patterns, trauma-induced physiological disturbances and subsequent clinical course and outcome.

STUDY PROCEDURES

Informed Consent (same as primary ACIT study)

The standard operating procedure for obtaining consent is included in appendix 2.

Primary Outcomes

Primary outcome is endogenous thrombin generation assessed via 10ml research blood sample collected within 60 minutes of arrival in the Emergency Department.

Secondary Outcomes

Secondary outcomes will include incidence of acute traumatic coagulopathy on arrival (defined by platelet count, prothrombin time, fibrinogen, fibrinolysis); admission blood lactate; admission clotting factor levels and markers of fibrinolytic activation/inhibition; quantitative analysis and phenotyping of microparticles; relative contributions of microparticle subtypes to thrombin generation.

Screening and recruitment

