All SWiFT trial adult patients (aged 16 and over) who are admitted to the emergency department at an MTC via a trauma team activation will be screened for eligibility to ACIT-ED. As most SWiFT patients will be incapacitated at the time of screening it is anticipated that a waiver of consent will be used followed by initiation of the informed consent process at a time appropriate from the participant as described in Section 9.1.

Schedule of study interventions

Study Activity	Emergency	Discharge/
	Department	Day 28
History and Physical	SWIFT data	
Demographics	SWIFT data	
Injury characteristics	SWIFT data	
Physiological	SWIFT data	
observations		
Adverse events	ACIT-ED	ACIT-ED
Blood Sampling*	ACIT-ED	
Clinical outcomes		SWIFT

^{*}All patients have one blood sample taken on admission at the same as routine clinical blood tests

Study Intervention

Blood samples

SWiFT trial patients co-enrolled into ACIT SWIFT will have a blood sample drawn to measure activation of coagulation, fibrinolysis, endothelial injury and the immune system. The maximum sample volume for the single blood draw on admission will be 20ml. Severe trauma patients not enrolled into either SWiFT or ACIT would normally have blood samples drawn at minimum at 0, 12 and 24 hours and daily thereafter.

As most major trauma patients have an arterial or central line placed, particularly during the first 24hours when the ACIT SWIFT sample may be taken it will not be painful to the patient. When this is not the case, we will coordinate our blood draw with those of clinical need whenever possible, to minimise number of needle-sticks. We will not be able to use blood that has already been collected and placed into specimen tubes as our samples will require specific handling and processing.

There will be no serial blood sampling during the bleeding episode and at 24hr, 72hrs and Day 7 as research resource will not enable robust data collection 24/7 when SWiFT patients will be arriving at the MTC. The initial post-dosing sample after the SWiFT intervention has been delivered is the most important sample. As the patients will be randomized we can determine how whole blood transfusion improves hemostasis through comparison between trial arms.

Additional data collection

There will be no additional data collected for ACIT SWIFT(outside of the SWiFT trial which will be responsibility of the SWiFT team).

Patient questionnaires

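### Section 9.4.2 gives a 10-year-old two incompatible blood-volume limits (5-10 ml and 20-30 ml); separately, the adult cut-off is worded in two ways at age 16

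*Protocol*

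**What the plan says.** Section 9.4.2 scales the volume of research blood to age because children have less blood in circulation. It gives three bands, each marked as a maximum: "Age 0-2 years: 1ml (maximum", "Age 3-10 years: 5-10ml (maximum" and "Age 10-15 years: 20-30ml (maximum". It also rules out prehospital sampling in children.

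Section 9.4.1, just before it, sets the sampling schedule and a general ceiling with no age attached: 40 ml at each time point, or 30 ml for samples taken during bleeding. The scheduled draws are at admission, 24 hours, 72 hours and day 7. Actively bleeding patients have further draws after the 4th, 8th and 12th units of red cells, if those are given.

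The adult boundary is worded in two ways in the main protocol. Section 9.2 has "All adult trauma patients (aged 16 and over) who are treated by London Air Ambulance". Section 9.4.1 has "Adult patients (>16 years old) treated by the London Air Ambulance medical team will have one additional sample". Appendix 4 (the ACIT SWIFT sub-study) does the same: its inclusion criteria say "Patients eligible for screening are adult (>16 years) trauma patients enrolled into the SWIFT prehospital randomized controlled trial", while its screening paragraph says "All SWiFT trial adult patients (aged 16 and over".

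**The concern.** The paediatric volumes are a safety limit for injured children who may be bleeding, and patients are enrolled under a waiver of consent by staff at several sites. Such a limit has to give one answer for each child. At age 10 it gives two, and both are stated as operative rules in the same list. Two sites could each follow the protocol to the letter and draw volumes that differ by a factor of three.

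The age-16 wording matters less but is also operative. It bears on whether a 16-year-old treated by the air ambulance has the extra prehospital sample, and on whether a 16-year-old in the SWiFT trial may enter the sub-study.

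**Working it through.** No design figure is involved, so there is nothing of the plan's own to reproduce. The check places each age, in completed years, against each rule.

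**Volume bands (Section 9.4.2)**

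| Age | Bands matched | Stated volume |
|---|---|---|
| 0-2 | one | 1 ml |
| 3-9 | one | 5-10 ml |
| 10 | two | 5-10 ml and 20-30 ml |
| 11-15 | one | 20-30 ml |

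At age 10 the first range ends at 10 ml and the second starts at 20 ml, so no volume lies in both. The ratio of the upper ends is 30 / 10 = 3. The lower boundary (0-2, then 3-10) has no shared age, so the list has no convention of shared endpoints that would settle the upper one. The general ceiling in Section 9.4.1 does not settle it either: 10 ml and 30 ml are both within 40 ml, and both within the 30 ml that applies during bleeding.

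**What the difference amounts to at age 10**

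Inputs: upper ends of 10 ml and 30 ml (Section 9.4.2); four scheduled draws plus up to three bleeding draws (Section 9.4.1). Total = number of draws × maximum per draw.

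- Limit cumulative: 10 ml or 30 ml in all.
- Limit per draw, four scheduled draws: 4 × 10 = 40 ml, or 4 × 30 = 120 ml.
- Limit per draw, all seven draws: 7 × 10 = 70 ml, or 7 × 30 = 210 ml. This requires a child who receives at least 12 units of red cells and is sampled at every time point, so it is an upper bound.

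The factor of three is the same in each case.

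**Adult boundary**

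| Place | Wording | Is a 16-year-old an adult? |
|---|---|---|
| Section 9.2 | 16 and over | yes |
| Section 9.4.2 | paediatric bands end at 15 | consistent with yes |
| Section 11.1, item [g] | parental consent for under-16s lacking capacity | consistent with yes |
| Section 9.4.1, prehospital sample | over 16 | no, in completed years |
| Appendix 4, study participants and inclusion criteria | over 16 | no, in completed years |
| Appendix 4, screening | 16 and over | yes |

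In the main protocol three places agree and Section 9.4.1 is the outlier. Its wording governs only the extra prehospital sample. In Appendix 4 the conflict is between inclusion and screening, so it touches eligibility itself. Every other age is classified the same way under both wordings.

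**The case against.** **The age-10 overlap is a slip that any reader would resolve.** A cautious reader might note that 10 ml breaches neither maximum. That works only if the lower ends of the ranges (5 ml and 20 ml) are treated as not binding, and the section does not say so. The overlap stands.

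**The basis of the limit is clear from context.** Section 9.4.2 follows a rule set per time point and describes an adjustment of it by age, which favours a per-draw reading. That is fair. The missing basis is a request for clarity and not a second contradiction, but for a protective limit it should be stated.

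**Over 16 may mean past the 16th birthday.** On that reading the age-16 mismatch almost disappears. The protocol does not say this and uses both wordings, so the point survives as a minor inconsistency.

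**A fix to Appendix 4 may have little practical effect.** The sub-study's proposed end date is June 2024 and this protocol version is dated July 2024. Entry also depends on enrolment in SWiFT, whose age limit is not shown. This lowers the weight of the Appendix 4 mismatch but does not remove it from the text.

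**Stronger readings that the document does not support.** A reader might infer that a 16-year-old falls under no volume rule. That does not follow: Section 9.4.2 is for children only, and in-hospital draws at 16 can be placed under the general ceiling in Section 9.4.1, which carries no age limit. A reader might also infer that the adult and child groups in Hypotheses 1D, 2D and 4B are affected. That is not shown: the over-16 wording in the main protocol governs the prehospital sample only, and Sections 9.2, 9.4.2 and 11.1 agree on the boundary between child and adult.

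**Conclusion.** The point holds in two parts of unequal weight.

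The main part is that the blood-volume limit for a 10-year-old is wrong as written. Two disjoint ranges apply and their maxima differ threefold. If the limits are per draw, the difference is 40 against 120 ml over the scheduled draws, and 70 against 210 ml at the extreme. If they are cumulative, it is 10 against 30 ml. It concerns 10-year-olds only, not children in general.

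The lesser part is the adult cut-off. If age is read in completed years, it is unclear whether a 16-year-old has the prehospital sample or may enter the sub-study.

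The Appendix 1 and 2 procedures are listed, but their text is not shown. They might settle practice at the sites, but they would not remove a contradiction in the protocol body. The point is an internal inconsistency in procedure and eligibility, with no effect on any sample-size figure. It should be corrected.

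**What to change.** - In Section 9.4.2, reconcile the bands so that each age has exactly one limit, and state whether that limit is per draw or cumulative.
- Use one adult/child wording in Sections 9.2 and 9.4.1 and in the study participants, inclusion and screening paragraphs of Appendix 4, and say that age is in completed years if that is meant.
- Check the blood-processing and consent procedures (Appendices 1 and 2) against the result.

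The clinical team must decide which volume limit and which age cut-off apply; this review proposes neither. The cost is wording in a few places, plus any matching change to the site procedures. Nothing in the design or the sample size needs to be redone.

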9.4.3 Muscle biopsies

Muscle biopsies will only be taken from adult patients undergoing surgical intervention, where the patient is anaesthetised and muscle is already exposed either by the incision or the traumatic injury itself (e.g. abdominal, chest or limb trauma). During the first seven days surgical procedures performed will be determined by clinical need and injured anatomy.

Muscle biopsies will be taken when the patient is undergoing emergency or planned surgery and serial samples will be collected from the exposed muscle during each surgical episode in the first seven days. Muscle tissues will be collected to enable extravascular tissue analysis to be performed to determine cellular responses to trauma and inflammation, in particular biomarkers for cellular death and activation of early signalling pathways within the cells which may have been initiated by the traumatic insult to the body.

A 1cm cube of muscle will be removed during the operation and immediately wrapped in saline-moistened gauze. The muscle biopsy can then be stored cool for several hours before being split to provide tissue for fixing in 4% glutaraldehyde (for visualisation/cell surveys) as well as snap frozen material (for histochemistry and biomarker analysis).

Cellular markers of inflammatory response will include T-cells, NK cells, Macrophages, B-cells and Eosinophils. Biomarkers of tissue damage and injury response will include TNF- α , IL-1 ,IL-6, IL-8, IL-10, Complement components, heat shock proteins, Syndecin-1, soluble thrombomodulin, mitochondrial DNA. Transcriptomic and proteomic studies will examine changes in cellular behaviour.

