Recent studies suggest that this late mortality due to MODS may be due to the body's responses to tissue damage and to blood loss that occur immediately following injury.(12) There is a significant body of both basic science and clinical evidence that implicates the activation and dysregulation of the coagulation and inflammatory systems in the development of MODS.(13) However, most of this data comes from research into sepsis which may not be directly translatable. The mechanisms for the activation of the relevant pathways in trauma, and their relationship to clinical disease and outcomes have yet to be delineated. Identification of these key pathways will provide new directions for drug development and perhaps a specific treatment for post-traumatic MODS, either through organ protection or organ restorative therapies.

We postulate two mechanisms for the activation of these systems in trauma: tissue damage itself, and cellular hypoperfusion.

Tissue damage

A number of studies including the first from our group at the Royal London Hospital, (14) have shown that trauma patients may arrive in the emergency department with severely deranged blood coagulation. (15) Significant tissue damage (in conjunction with severe blood loss) results in a reduced ability to form and maintain clots, leading to further bleeding, through an endogenous process termed acute traumatic coagulopathy (ATC). (16) Patients with this coagulopathy are three to four times more likely to die than those without. (7, 14) The incidence of coagulopathy was closely related to the severity of injury, and not to the volumes of fluid administered, suggesting that the injury load itself was responsible for the activation

of the coagulation systems. The precise mechanisms by which tissue injury activates the coagulation and inflammatory systems have yet to be fully characterised.

Tissue hypoperfusion / hypoxia

Ischemia following haemorrhagic shock is known to lead to MODS and increased mortality.(11) Several studies have shown that the severity of shock on admission correlates with eventual outcome. The duration of tissue ischemia, as measured by base deficit and lactate, and even sub-clinical tissue ischemia which persists for over 12 hours has a mortality is 38%, over twice that of patients who do not suffer a prolonged ischemic episode.(17) Tissue hypoxia leads to endothelial injury and priming of cellular and humoral components of the inflammatory pathways.(18)

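### Section 9.4.3 lets excised muscle wait for hours before it is frozen, with no stated limit or time record, so handling change may be inseparable from the response to trauma

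*Protocol*

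**What the plan says.** Section 9.4.3 sets out the handling of muscle in order. At operation, "A 1cm cube of muscle will be removed during the operation and immediately wrapped in saline-moistened gauze". Next, "The muscle biopsy can then be stored cool for several hours before being split to provide tissue for fixing in 4% glutaraldehyde", and the sentence goes on to name the second product of that split: "as well as snap frozen material (for histochemistry and biomarker analysis". The fixed and the frozen portions are thus both made after the cool storage. No portion is described as preserved at excision.

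The same section states what the tissue is for: "in particular biomarkers for cellular death and activation of early signalling pathways within the cells which may have been initiated by the traumatic insult". It lists cytokines, heat shock proteins and mitochondrial DNA among the markers, and adds: "Transcriptomic and proteomic studies will examine changes in cellular behaviour". Sampling is repeated: "serial samples will be collected from the exposed muscle during each surgical episode in the first seven days".

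Section 14.3 has samples processed and stored at the enrolling centre at -80°C, labelled with study identifier, sample type and time point. For preparation and storage it refers to Appendix 1, which the appendix list in section 19 titles as a blood processing SOP. Section 14.1 (Central Laboratories) says that procedures will be documented in a laboratory manual. The text of neither is shown.

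**The concern.** Muscle cut from the body has no perfusion. Cooling slows what happens next but does not amount to freezing or fixation. Markers of cell death, stress signalling and transcript levels are the kinds of read-out that can continue to move until the tissue is preserved.

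The difficulty is sharper here because the study's own exposure is of the same kind. Section 5.1 names cellular hypoperfusion as one of two postulated mechanisms and says: "Tissue hypoxia leads to endothelial injury and priming of cellular and humoral components of the inflammatory pathways". Hypothesis 2B concerns the degree and duration of hypoperfusion. A wait of unknown length after excision adds a further period without blood flow to tissue that is meant to show what happened in the patient.

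What is at stake is the interpretation of the muscle results. If the delay varies, some of the variation in a marker may come from handling. If the delay also differs between the samples being compared, part of an apparent difference may be handling as well, and could be reported as an activated pathway.

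**Working it through.** The protocol states no figure for this point. It gives no delay in minutes, no assay variance, no drift rate and no number of biopsies, so there is nothing to reproduce or recompute. The check is a reading of the sections against each other.

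1. **Does the delay apply to the molecular portion?** Yes. In section 9.4.3 the split comes after the cool storage, and the snap-frozen material for biomarker analysis is one of the two products of the split.

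2. **Is the delay bounded?** Not in the protocol text. Section 9.4.3 speaks of hours without a number and of cool without a temperature. Section 14.3 gives the final storage temperature but no time from collection to freezing. Appendix 1 is a blood procedure by title.

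3. **Is the delay stated to be recorded?** No. The label items in section 14.3 are identifier, sample type and time point. A sampling time point does not give the interval from excision to freezing, and no section shown asks for both times.

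4. **Are the read-outs sensitive in principle?** The section's stated targets are cell death and early signalling, with transcriptomic and proteomic work. These describe the state of the cells at the moment of preservation. Under the rule as written, that moment may be hours after excision.

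5. **Can the two sources be separated afterwards?** Write a measured marker as M = T + h(t) + e. T is the in vivo level at excision, h(t) is the change over the delay t, and e is measurement error. With t unrecorded and no aliquot preserved at excision, T and h(t) are not separately identifiable. For two groups or two occasions A and B, the expected difference is (T_A - T_B) + (mean h_A - mean h_B). If the delays have the same distribution and drift acts alike in both, the second term is zero and the wait adds mainly noise. If they differ, the second term is bias.

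6. **Could delays differ between compared samples?** They could. Section 9.4.3 takes samples at both emergency and planned operations and repeats them over the first seven days. Section 4 lists four hospitals, and section 14.3 has each centre process its own samples. The documents do not show that delays do differ, or in which direction.

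7. **Could an analysis plan repair this?** Only if the times exist. A covariate that was never collected cannot be used, so the point belongs in the protocol.

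**The case against.** The strongest reply has five parts.

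**The wording is permissive.** Section 9.4.3 allows the wait and does not require it, and the tissue is kept cool. This stands. It is why the conclusion is that handling change may be mixed in, not that it is. A site that waits for hours would nevertheless be following the protocol.

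**The laboratory manual may hold a limit and a time log.** This stands in part. It rules out saying that the delay is unlimited or unrecorded in practice. It does not remove the fault, because the protocol expressly permits the wait and a stricter manual would then be at odds with it.

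**A link with severity is conjecture.** A reader might infer that the wait is longest in emergency or out-of-hours surgery, and so in the most severely injured, and that an emergency-versus-planned contrast is therefore biased. The documents support neither step. They give no delays by urgency or hour, and section 9.4.3 names emergency and planned surgery only as occasions for sampling, not as groups to be compared.

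**Any number would be assumed.** A reader might attach a false-positive rate. Suppose a drift of 0.1 to 0.3 SD per hour and a 2-hour difference in delay, so d = 0.2 to 0.6 SD. Then Phi(d × sqrt(n/2) - 1.96) gives 17%, 52% and 85% for d = 0.2, 0.4 and 0.6 with 50 biopsies per group, and 29%, 81% and 99% with 100. The arithmetic is right, but drift, delay gap and group sizes are all assumptions, so the range of 17% to 99% only restates them. It is not an estimate of bias in this study.

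**Dropping late samples could itself bias the results.** If delay were related to the type of patient, a rule removing over-limit specimens from molecular work would select patients out. This stands, and it shapes the fix.

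**Conclusion.** The point holds as a poorly fixed handling rule. The protocol permits a wait of hours before freezing, sets no maximum and does not ask for the delay to be recorded, for tissue whose planned read-outs can change during that wait. Ex vivo change may then be inseparable from the in vivo response.

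Bias in serial or between-patient comparisons would further require that delay, or its effect, differs between the samples compared. That is possible under the rule but not documented. The conclusion also assumes that cool storage slows change without stopping it, and that no unseen document already sets a limit. The size is unknown and cannot be derived from what the protocol gives.

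The reach is limited. Section 8 has muscle taken in some patients only, and muscle markers are not among the outcomes in sections 6.2 and 6.3. A reader might take the point as a threat to the study's main results, but nothing in the documents supports that. It is a cheap improvement to the exploratory muscle work, and worth making now because recruitment is open-ended (section 4) and a delay that was not recorded may not be recoverable later.

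**What to change.** Amend the storage sentence in section 9.4.3 as follows.

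- Divide the cube at collection. Snap-freeze the portion for cell-death, signalling, transcript and protein work at excision, or as soon as possible within a maximum time that the protocol states.
- Allow cool storage only for the portion to be fixed.
- Record the time of excision and the time of freezing for every specimen.
- Use the delay as a covariate in analyses of muscle markers, with a sensitivity analysis that leaves out over-limit specimens. Do not exclude them automatically, since that could select patients out.
- Align the laboratory manual with this text, and give muscle its own preparation guidance or state where it is, since Appendix 1 is titled for blood.

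The cost is cold transport available in theatre and two data fields per specimen. For specimens already held, retrieve the times from theatre and laboratory records where they exist, and otherwise report the delay as unknown.
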